1.0 PROTOCOL SUMMARY AND/OR SCHEMA

This is a single arm open label phase 2 study evaluating the potential effect of ixazomib on the prevention of recurrent or late acute graft-versus-host disease (GVHD) and chronic GVHD at 1-year following reduced intensity (RI) or non-myeloablative (NMA) allogeneic hematopoietic stem cell transplantation (HSCT) for the treatment of hematologic malignancies. Patients will be eligible for enrollment if they are without active acute or chronic GVHD between days +100 and +150 following HSCT. After enrollment patients will initiate treatment with ixazomib and continue until all immunosuppressants are tapered off or 1 year post-HSCT is reached (whichever occurs first) or grade II-IV acute and/or chronic GVHD develops or malignant disease relapse/ progression occurs. The primary aim is to assess the incidence of development of grade II-IV recurrent or late acute GVHD (aGVHD) and chronic GVHD (cGVHD) at 1-year following ixazomib administration post-HSCT. Calcineurin inhibitor based drug and methotrexate (MTX) will be used for initial GVHD prophylaxis. Ixazomib will be used as secondary GVHD prophylaxis as above.

Patients will be monitored post-transplant for incidence and severity of recurrent or late acute and cGVHD at 1-year post-HSCT, transplant-related mortality (TRM), characteristics of immune recovery, as well as overall and event-free survival.

Protocol Schema

Ixazomib
4 weeks cycles
(3 weeks on/ 1 week off)

+100 to +1 year

Ixazomib 4 mg PO once a week. Cycles are every 28 days (3 weeks on/ 1 week off) until discontinuation of immunosuppressants or 1 year post-HSCT (whichever occurs first), or grade II-IV acute or chronic GVHD develops or malignant disease relapse/ progression occurs.

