9.2 GVHD prophylaxis

Ixazomib beginning between day +100 to +150 at a dose of 4 mg orally once per week (3 weeks on/ 1 week off). The patients will continue on this same dose until taper off from immunosuppressants or 1 year post-HSCT is reached (whichever occurs first) or until the patient develops GVHD or malignant disease relapse/progression occurs. Patients who reach 1 year post-HSCT or discontinue immunosuppressants mid-cycle should complete their current cycle of ixazomib.

- The levels of the drug will not be monitored while the patients are on study.
- In order for patients to receive drug, they must have a platelet count > 75K, Hgb (untransfused) > 8 and an ANC > 1.0 (can be supported with G-CSF)
- If more than 2 doses in a row or more than 3 doses total are held, the patient is removed from study.
- Doses are given weekly +/- 3 days

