9.1.1 Dose-modification guidelines

Treatment with ixazomib will use a cycle length of 28 days. For a new cycle of treatment to begin, the patient must meet the following criteria:

- ANC \geq 1,000/mm³
- Platelet count \geq 75,000/mm³
- Serum creatinine \leq 2.5 mg/dL and less than double from pre-treatment evaluation value

If the patient fails to meet the above-cited criteria for initiation of the next cycle of treatment, dosing should be delayed for 1 week. At the end of that time, the patient should be re-evaluated to determine whether the criteria have been met. If the patient continues to fail to meet the above-cited criteria, delay therapy and continue to re evaluate. The maximum delay before treatment should be discontinued will be 4 weeks or at the discretion of the Principal Investigator.

Ixazomib dose adjustments:

Dose Level	Dose (mg)
Starting Dose	4.0 mg
-1	3.0 mg
-2	2.3 mg

Table 9.1.1 Ixazomib dose adjustments for hematologic toxicities

Criteria	Action
Within-Cycle Dose Modifications	

 If platelet count $\leq 30 \times 10^9/L$ or ANC $\leq 0.50 \times 10^9/L$ on ixazomib dosing day (other than Day 1) If serum creatinine $> 2.5 \text{ mg/dL}$ or has doubled from pre-treatment evaluation 	
 Ixazomib dose should be withheld. Complete blood count (CBC) with differential should be repeated until the ANC and/or platelet counts have exceeded the prespecified values. Upon recovery, ixazomib may be reinitiated with 1 dose level reduction.
Dose Modifications for Subsequent Treatment Cycles	

 Delay of > 2 weeks in the start of a subsequent cycle due to lack of toxicity recovery as defined in Section 9.1.1 ANC $< 1.0 \times 10^9/L$, platelet count $< 75 \times 10^9/L$, serum creatinine $> 2.5 \text{ mg/dL}$, serum creatinine doubled from pre-treatment evaluation, or other nonhematologic toxicities $>$ Grade 1 or not to the patient's baseline condition 	
 Hold ixazomib until resolution as per criteria Section 9.1.1 Upon recovery, reduce ixazomib 1 dose level. The maximum delay before treatment should be discontinued will be 3 weeks or at the discretion of the PI.
Dose Modifications for Subsequent Treatment Cycles	

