9.1.2. Excluded concomitant medications and procedures

The following medications and procedures are prohibited during the study.

Systemic treatment with any of the following metabolizing enzyme inhibitors is not permitted in this study. A DDI with a strong inhibitor would increase the ixazomib exposure and could lead to a higher probability of an AE:

- Strong inhibitors of CYP1A2: fluvoxamine, enoxacin, ciprofloxacin
- Strong inhibitors of CYP3A: clarithromycin, telithromycin, itraconazole, voriconazole, ketoconazole, nefazodone, and posaconazole.

Systemic treatment with any of the following metabolizing enzyme inducers should be avoided, unless there is no appropriate alternative medication for the patient's use (rationale: Unlike with inhibitors, if there were to be a DDI with an inducer, ixazomib exposure would be less; therefore, there would be a reduced chance of an AE. However, there may be less chance for an antitumor effect, but that is not an absolute reason to be taken off ixazomib):

- Strong CYP3A inducers: rifampin, rifapentine, rifabutin, carbamazepine, phenytoin, and phenobarbital.
- Exclude foods and dietary supplements include St. John's wort and Ginkgo biloba.

The following procedures are prohibited during the study:

- The addition of immunosuppressant(s) and/or GVHD prophylactic agents once enrolled in the study.
- Platelet transfusions to help patient meet eligibility platelet level criteria are not allowed within 3 days prior to study drug dosing for any dosing day.

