10.0 EVALUATION DURING TREATMENT/INTERVENTION

All patients will be closely monitored and evaluated as per MSKCC BMT standard of care guidelines. Study specific assessment schedule listed in table below.

Evaluation includes history and physical examination, blood count, chemistry including liver function test at screening, 6 months and 12 months post-allograft. Blood counts and blood chemistries will be monitored before the initiation of each treatment cycle and prior to the third dose of cycles 1 and 2.

Toxicity assessment will be performed monthly during the duration of treatment or discontinuation of the study drug. Prior to initiating the first two cycles, toxicity assessments will be performed at MSKCC's main campus when feasible. Toxicity assessments for subsequent cycles can be collected via phone call.

Acute and chronic GVHD will be diagnosed and graded according to established criteria^{5,25}. Assessments will be obtained at approximately at day 100, 6 months, and 12 months. Additional time points will be done if clinically indicated.

Scheduled Study Assessments:

Procedures	Study time-points					
	Consent	Pre-Treatment Evaluation	Ixazomib Cycles 1-9	6 months post-HSCT	12 months post-HSCT	Safety Follow Up
Window	100 – 150 days post-HSCT	- 30 days prior to Dose 1	+/- 3 days	+/- 14 days	+/- 30 days	30 days after last treatment +/ - 7 days
Informed consent	X					
History/ Physical		X		X	X	
Karnofsky score		X				
CBC ¹		X	X			
Blood Chemistry/ CMP ¹		X	X	X	X	
Thyroid function test ²		X		X	X	
EKG		X				
Pregnancy test (if applicable)		X				
Urinalysis		X				
Immune function testing ³		X		X	X	
GVHD evaluation	X			X	X	
Toxicity assessment ⁴		X	X	X	X	X

¹ CBC and Chemistry are required prior to dose 1 and dose 3 for the first 2 cycles and then prior to first dose of each subsequent drug cycle

² Thyroid function test should include thyroid stimulating hormone (TSH) and free T4

³ Immune function testing is performed per institutional practice and is recommended at indicated study time points.

⁴ To be collected prior to first dose of each cycle.

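### Laboratory hold rules cover doses 2 and 3 of each cycle, but over nine cycles the schedule requires a blood test before only 2 of those 18 doses, and two sections set different thresholds

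*Combined protocol and SAP*

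**What the plan says.** Treatment is weekly: "Cycles are every 28 days (3 weeks on/ 1 week off"), so three doses per cycle. The section 10 table has a column headed "Ixazomib Cycles 1-9".

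Three places set laboratory conditions on dosing:

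- Section 9.2 (GVHD prophylaxis): "In order for patients to receive drug, they must have a platelet count > 75K", together with untransfused hemoglobin above 8 and ANC above 1.0. The sentence is not limited to the start of a cycle.
- Section 9.1.1, cycle start: ANC at least 1,000/mm³, platelets at least 75,000/mm³, and limits on serum creatinine.
- Table 9.1.1, within a cycle: the dose is withheld for platelets at or below 30 × 10⁹/L or ANC at or below 0.50 × 10⁹/L "on ixazomib dosing day (other than Day 1"). A second bullet gives a creatinine hold (above 2.5 mg/dL, or doubled) without naming the dosing day.

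Section 10 sets the required tests. Its text says "Blood counts and blood chemistries will be monitored before the initiation of each treatment cycle and prior to the third dose of cycles 1 and" (the sentence ends with the second cycle), and footnote 1 to the table says the same: "required prior to dose 1 and dose 3 for the first 2 cycles and then prior to first dose of each subsequent drug cycle". The text also states: "Evaluation includes history and physical examination, blood count, chemistry including liver function test at screening, 6 months and 12 months post-allograft". In the table as extracted, the CBC row has no mark at the 6- and 12-month visits, while the chemistry row does.

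**The concern.** A rule that withholds a dose on a count needs a count. From the required tests alone, dose 2 of every cycle, and dose 3 from cycle 3 onward, have no current value to which the rule can be applied. Table 9.1.1 also directs how to adjust the dose for hematologic toxicity that arises and resolves within a cycle. From cycle 3 on, no dose-linked test falls between one Day 1 and the next, so detecting such toxicity depends on tests done for other reasons.

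This is a safety matter first, but it also reaches the trial's data. Under section 9.2, more than 2 consecutive or more than 3 total held doses remove the patient from study. Under section 12.3, permanent discontinuation for drug-related toxicity is a primary-endpoint failure. Whether a hold is recorded therefore depends partly on whether a discretionary test was done, and on which of two thresholds the clinician applied.

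**Working it through.** **Inputs.** Doses per cycle: 3 (section 1.0). Scheduled cycles: 9 (section 10 table). Required pre-dose tests: 2 in each of cycles 1 and 2, then 1 per cycle (section 10 text and footnote 1).

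**Check of the nine cycles.** Starting on day 100 and stopping at day 365, the number of complete 28-day cycles is (365 − 100)/28 = 9.46, so 9. This agrees with the table.

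**Required tests over c cycles.** Doses = 3c. Tests = 2 × min(c, 2) + max(c − 2, 0). Doses after Day 1 = 2c, of which min(c, 2) have a required test.

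For c = 9: doses = 27; tests = 2 × 2 + 7 = 11 (41%); doses without a required test = 27 − 11 = 16 (59%). Doses after Day 1 = 18; with a required test = 2; without = 16 (89%).

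| Cycles given | Doses with a required test | Share | Doses after Day 1 with a required test |
|---|---|---|---|
| 1 | 2 of 3 | 67% | 1 of 2 |
| 2 | 4 of 6 | 67% | 2 of 4 |
| 3 | 5 of 9 | 56% | 2 of 6 |
| 4 | 6 of 12 | 50% | 2 of 8 |
| 5 | 7 of 15 | 47% | 2 of 10 |
| 6 | 8 of 18 | 44% | 2 of 12 |
| 7 | 9 of 21 | 43% | 2 of 14 |
| 8 | 10 of 24 | 42% | 2 of 16 |
| 9 | 11 of 27 | 41% | 2 of 18 |

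So a majority of doses lack a required test only from five cycles on. Among doses after Day 1, half are covered at one or two cycles and a minority from three.

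**Thresholds side by side, for a dose after Day 1.**

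| Value | Section 9.2 (GVHD prophylaxis) | Table 9.1.1, within cycle |
|---|---|---|
| Platelets (× 10⁹/L) | must exceed 75 | withhold at 30 or below |
| ANC (× 10⁹/L) | must exceed 1.0 | withhold at 0.50 or below |
| Hemoglobin | must exceed 8, untransfused | no rule |
| Creatinine | no rule | withhold above 2.5 mg/dL or if doubled |

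With platelets above 30 and up to 75, or ANC above 0.50 and up to 1.0, section 9.2 read literally denies the dose and Table 9.1.1 does not withhold it. A dose in that band would count toward the held-dose removal rule under one reading and not under the other.

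**The case against.** The strongest reply is that the table gives only study-specific assessments. Section 10 opens by placing all patients under the institution's transplant guidelines, section 9.1 does the same, and section 9.2.4 provides for further testing by standard practice. Those guidelines are not in the documents and may well supply frequent counts. Table 9.1.1 is conditional: it acts on a value if there is one and does not order a test. Day 1 of every cycle is tested against the higher limits. This stands in part. It rules out saying that doses after Day 1 go unmonitored or that the hold cannot work. It does not remove the gap, because none of these provisions ties a test to a dosing day, and section 9.2.4 itself refers back to the protocol's schedule for regular counts.

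Second, section 9.2 can be read as a cycle-start condition, since its limits nearly match those of section 9.1.1 and would otherwise make the Table 9.1.1 count hold redundant. That reading is coherent, but the sentence does not say so.

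Third, nine cycles is the full schedule, not what every patient will receive. Treatment stops at GVHD, relapse or completed taper, and the design contrasts GVHD incidences of 40% and 60%. If a sibling-donor taper of 10–25% every 2 weeks is taken in decrements of the starting dose, begins together with ixazomib, and leaves no other immunosuppressant (all assumptions), it lasts 4 to 10 steps × 2 weeks = 8 to 20 weeks, or 2 to 5 cycles. This stands, and is why the results are given by number of cycles.

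**Conclusion.** The mismatch is real. Over nine cycles, 16 of 27 doses, all of them doses after Day 1, carry a laboratory hold rule with no required value to apply it to; the share is smaller for patients who stop early. The count assumes three doses per cycle without omissions and covers protocol-required tests only. Two smaller inconsistencies accompany it: the differing within-cycle thresholds, and the 6- and 12-month blood counts that appear in the text but not in the CBC row as extracted (a blank cell may be an artifact of reading the table).

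A reader might go further in several ways that the documents do not support:

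- *The oral single-agent rates of 34% thrombocytopenia and 14% neutropenia measure missed holds.* They are treatment-emergent event rates without a grade restriction. No rate is given for crossing the hold thresholds, so the number of missed holds is unknown.
- *The creatinine hold explicitly applies on each dosing day.* Its bullet does not say so, and section 9.2 does not list creatinine.
- *The transfusion restriction in section 9.1.2 also needs a test.* Platelet transfusions "are not allowed within 3 days prior to study drug dosing for any dosing day" is a limit on timing, and complying with it needs no laboratory value.
- *The graft-failure stopping boundary is undermined.* That boundary counts failures against patients accrued; it does not define how long or how often each patient is tested.
- *A tenth cycle would have no tests.* Footnote 1 covers every later cycle, whatever the column heading says.

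**What to change.** Reconcile section 9.2 (GVHD prophylaxis), section 9.1.1 with Table 9.1.1, and section 10 (text, table and footnote 1) so that:

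1. it is clear which laboratory rule governs doses after Day 1;
2. each such rule either has a required value in the schedule, or the protocol states how it applies when no test is scheduled;
3. holds based on unscheduled results are kept;
4. the CBC row agrees with the section 10 text at 6 and 12 months.

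Which thresholds apply, and whether the schedule or the rules change, is a clinical decision for the sponsor; no threshold or test frequency is proposed here.

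The cost is one amendment. If the sponsor chose to require a test before every dose, the upper bound is 27 − 11 = 16 additional routine draws for a patient who completes nine cycles, less any already done as standard care. If the sponsor instead clarifies the rules, the cost is wording only.

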11.0 TOXICITIES/SIDE EFFECTS

11.1 Toxicity Grading

Toxicities will be graded on a scale of 0 to 4 as described by the NCI- Common Terminology for Adverse Events (CTCAE), version 4.0.

11.2 Ixazomib

Ixazomib may cause fatigue, thrombocytopenia, nausea, vomiting, diarrhea, decreased appetite. Less frequently the drug can cause rash, peripheral edema, and neutropenia. Further details of management of ixazomib-related hematologic toxicity AEs are described in Section 9.1.1.

Treatment modifications due to ixazomib-related AEs are outlined in Table 11.2.

Table 11.2 Ixazomib treatment modification (delays, reductions, and discontinuations) due to adverse events (non-hematologic toxicities)

Adverse Event (Severity)	Action on Study Drug	CTCAE Description
Peripheral Sensory		
Neuropathy:		
Grade 1 peripheral sensory neuropathy	
 • No action 	Grade 1: Asymptomatic; loss of deep tendon reflexes or paresthesia
Grade 2 peripheral sensory neuropathy	
 • Hold study drug until resolution to Grade ≤ 1 or baseline • Once recovered, resume study drug at same dose 	Grade 2: Moderate symptoms; limiting instrumental ADL
Grade 3 peripheral sensory neuropathy	
 • Hold study drug until resolution to Grade ≤ 1 or baseline • Reduce study drug to next lower dose upon recovery 	Grade 3: Severe symptoms; limiting self care ADL
Grade 4 peripheral sensory neuropathy	
 • Discontinue study drug 	Grade 4: Life-threatening consequences; urgent intervention indicated
Nervous System Disorder:		
Grade 1 nervous system toxicity judged to be related to study drug	
 • No action 	Grade 1: Asymptomatic or mild symptoms; clinical or diagnostic observations only; intervention not indicated
Grade 2 nervous system toxicity judged to be related to study drug	
 • Hold study drug until resolution to Grade ≤ 1 or baseline 	Grade 2: Moderate; minimal, local or noninvasive intervention indicated; limiting age appropriate instrumental ADL
New or worsening grade 2 or grade 3 or 4 toxicity judged to be related to study drug	
 • Discontinue study drug 	Grade 3: Severe or medically significant but not immediately life-threatening; hospitalization or prolongation of existing hospitalization indicated; disabling; limiting self care ADL

Table 11.2 Ixazomib treatment modification (delays, reductions, and discontinuations) due to adverse events (non-hematologic toxicities)

Adverse Event (Severity)	Action on Study Drug	CTCAE Description
		Grade 4: Life-threatening consequences; urgent intervention indicated
Grade 2 Rash	
• Symptomatic recommendations. The investigator and project clinician may discuss considerations for dose modifications and symptom management.	Grade 2: Rash covering 10-30% BSA with or without symptoms; limiting instrumental ADL
Grade \geq 3 nonhematologic toxicity judged to be related to study drug	
• Hold study drug until resolution to Grade \leq 1 or baseline• Reduce study drug to next lower dose upon recovery	
If not recovered to Grade \leq 1 or baseline within 4 weeks	
• Discontinue treatment	

12.1 CRITERIA FOR THERAPEUTIC RESPONSE/OUTCOME ASSESSMENT

12.2 Criteria for therapeutic response for the primary endpoint

The primary aim is to assess the efficacy of ixazomib for the prevention of recurrent or late grade II-IV aGVHD or chronic GVHD by 1-year post-transplant. Therapeutic response will be determined by the absence of grade II-IV aGVHD or chronic GVHD diagnostic features (or any of the other failure criteria listed in 12.2) during the study window

Patients who receive at least one cycle of therapy will be considered evaluable for the primary endpoint.

12.3 Criteria for treatment failure for the primary endpoint

- Study drug is discontinued and unable to resume due to drug related toxicity.
- New onset or recurrence of grade II-IV aGVHD (including GVHD flares).
- New onset of chronic GVHD.
- Administration of systemic therapy for treatment of GVHD.
- Development of secondary graft failure during the administration of the study drug.
- Mortality (transplant or treatment-related)

If treatment failure criteria is met, the patient will be removed from the study. A 30-day follow-up will be conducted for end-of-treatment evaluation for toxicity assessment. This follow-up may be conducted via phone call or in-person by the clinical team.

12.4 Outcome assessment

12.3.1 Graft-versus-host disease (GVHD)

Acute GVHD will be diagnosed clinically and histological assessment will be obtained where possible. Grading of aGVHD will be based on IBMTR criteria²⁵. Acute GVHD will be assessed at Day 100 at a consensus review. Recurrent aGVHD will be defined as the reappearance of aGVHD symptoms after day 100 whereas late acute GVHD will be defined as aGVHD occurring after day 100. Chronic GVHD will be diagnosed and graded according to consensus criteria⁵. Patients will be assessed for development of GVHD at 6 months and 12 months post-allograft. Assessments will evaluate the severity of symptoms and signs caused by GVHD and possible confounding factors. Additional assessments may be conducted if clinically indicated.

12.3.2 Secondary graft failure

Secondary graft failure is loss of ANC to < 500/ μ L for 14 consecutive days after initial recovery or loss of donor chimerism to < 10% donor after primary donor engraftment has been achieved not due to progressive malignancy within the marrow.

Patients with suspected graft failure will be evaluated with bone marrow biopsy to assess BM cellularity and assess for residual or recurrent disease, and molecular analyses of marrow.

12.3.3 Transplant related mortality (TRM)

TRM is defined as death at any time from the commencement of the study trial due to any cause other than disease relapse with the exception of automobile or other accidents. The incidence of TRM from the enrollment on protocol to 1 year after HSCT is a secondary endpoint of the study.

12.3.4 Disease progression

Relapse of malignancy or progression of disease from the base-line documented pre-HSCT, is a secondary endpoint of this study and will be defined by an increasing number of malignant cells of recipient origin in the marrow over 5%, by the presence of circulating malignant cells, pathologic lymphadenopathy or by the presence of malignant cells at any other site. Radiologic studies, flow cytometric analysis or molecular studies of the marrow and/or peripheral blood, and/or biopsy of lymph nodes or other sites may also be obtained for the diagnosis of relapse or disease progression.

12.3.5 Immunologic recovery and immunization

Immune recovery will be performed at serial time points after transplant per standard of care as indicated in section 10. All time points will guide clinical decisions and be billable unless they are collected after a patient has completed immune recovery as marked by the initiation of vaccinations. Patients may be re-immunized from 12 months post-transplant according to the CDC guidelines. Percentage of patients who get vaccines on time and response to vaccination will be documented.

Patients who meet criteria for immunization (CD4 T cell > 200cells/ μ L, CD19 B cells > 50 cells/ μ L, IgG > 500 mg/dL, > 8 weeks after last dose of IVIG, > 6 months after last dose of Rituximab) will have pre-immunization titers measured and will be immunized according to institutional guidelines. Post-vaccine titers will be obtained to evaluate for vaccination response which is defined as at least a fourfold rise in specific antibody levels or a rise to a level considered protective per standard BMT practice.

